At each therapy session, participants will complete the PCL-5 (Weathers et al., 2013) and TLFB (Sobell & Sobell, 1996) in order to assess self-reported PTSD symptomatology, opioid use, illicit and licit non-opioid drug use, alcohol use, and access to support services. Therapy sessions may be conducted in-person or remotely via Zoom platform. At 4-, 8-, and 12-weeks post-randomization, all participants will complete follow-up assessments consisting of an abbreviated version of the intake and participants randomized to receive PET will also complete the Working Alliance Inventory Client Form (WAI; Horvath & Greenberg, 1989). A participant satisfaction questionnaire will also be administered at Week 12. Follow-up assessment visits will be conducted in-person at our clinic at UHC. However, study measures may also be administered remotely via phone or Zoom platform. Furthermore, if a participant is at high-risk and/or currently experiencing COVID-19 symptoms, urine collection may be excused and study measures can be administered remotely via phone or Zoom platform. Regardless of experimental group, all participants will receive \$60 for completing the initial intake assessment and \$150 for completing follow-up assessments at 4-, 8-, and 12-weeks post-randomization.

For research involving survey, questionnaires, etc.: Describe the setting and the mode of administering the instrument and the provisions for maintaining privacy and confidentiality. Include the duration, intervals of administration, and overall length of participation.

Not applicable

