Statistical Considerations: Delineate the precise outcomes to be measured and analyzed. Describe how these results will be measured and statistically analyzed. Delineate methods used to estimate the required number of subjects. Describe power calculations if the study involves comparisons. Perform this analysis on each of the primary and secondary objectives, if possible.

Statistical Methods

The three experimental groups will be compared on baseline characteristics using analyses of variance for continuous variables and chi-square tests for categorical variables. If characteristics differ significantly and are predictive of outcome, they will be considered as potential covariates in subsequent analyses. Primary analyses will include all randomized subjects independent of early dropout, consistent with an intent-to-treat approach (Armitage, 1983). For our primary outcome of PTSD severity (CAPS-5) and secondary outcomes of psychiatric distress (BDI, BAI) and drug use (e.g., ASI subscales), mixed-models repeated measures analyses with subjects as random effects (SAS, PROC MIXED) will be used to compare the three groups across Week 4, 8, and 12 assessments. Fixed factors will include treatment condition and the within-subject factor, assessment timepoint, along with their interaction. Linear contrasts will be used to compare experimental conditions on changes from baseline to post treatment assessments, partial F-tests will be used to examine simple effects and pairwise comparisons will be based on Fisher's Protected LSD.

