For the primary outcome of PTSD symptom severity, we hypothesize that participants randomized to the OAT+PET+ condition will demonstrate greater decreases in PTSD severity relative to those randomized to the OAT or OAT+PET conditions. We also hypothesize that OAT+PET+ participants will demonstrate greater decreases in psychiatric distress as measured by the BAI and BDI relative to the other conditions. Additional secondary outcomes will be exploratory in nature and include PTSD trauma type as well as measures of opioid treatment response (e.g., OAT retention, illicit opioid abstinence, opioid craving). For example, repeated measures analyses for dichotomous data based on generalized estimating equations utilizing a logit link function (SAS, PROC GENMOD) will be used to compare groups on percentage of participants retained in OAT and abstinent for illicit opioids across Week 4, 8, and 12 assessments, with post hoc testing based on Wald chi square tests. Analyses will be performed using SAS Statistical Software V9.4 (SAS Institute, Cary, NC). Statistical significance will be determined based on $p < .05$ for all analyses.

Sample Size Justification

The proposed sample of 135 participants for the randomized trial is based on having sufficient power for detecting group differences on the primary outcome of mean PTSD symptom severity score (CAPS-5). Power is estimated to be 80% using $\alpha = .05$ to detect a difference in the mean change from baseline to Week 12 between any two groups of 8 points on the CAPS-5. These estimates are based on prior studies of PET in patients with concomitant SUD (Mills et al., 2012; [name] et al., 2018; Schacht et al., 2017), with slightly greater reductions expected in our OAT+PET+ condition as it is more intensive than the interventions used in those trials. For secondary outcomes, power is estimated to be 80% for detecting 12-week differences in mean change scores between groups of 9 units on the PCL-5, 6 units on the BDI, and 8 units on the BAI, both of which are smaller than the differences observed in a prior study with a similar sample ([name] et al., 2018). The estimated mean differences corresponding to 80% power using $\alpha = .05$ for detecting group differences on ASI subscales are Employment=.119, Psych=.113, Family/Social=.083, Alcohol=.048, Medical=.179, Legal=.065, and Drug=.083.

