Adverse Event, Unanticipated Problem (UAP), Reportable New Information (RNI): Describe how events and UAPs will be evaluated and reported to the IRB. All protocols should specify that, in the absence of more stringent reporting requirements, the guidelines established in the "Adverse Event and Unanticipated Problems Reporting Policy" will be followed. The UVM/UVM Medical Center process for review of adverse events and UAPs to subjects or others should be included in the DSMP.

AEs and SAEs will be assessed at each clinic visit by a trained RA or research therapist. Any SAE will be brought to the attention of the PI as soon as possible and not longer than 24 hrs. Any SAE, whether or not related to study intervention, will be reported to the IRB's CHRBSS using the UVM Adverse Event Reporting Document within 5 days of the event. The CHRBSS will determine whether additional reporting requirements are needed. Any SAEs will also be summarized in the yearly IRB continuing review, including a review of frequency and severity.

Withdrawal Procedures: Define the precise criteria for withdrawing subjects from the study. Include a description of study requirements for when a subject withdraws him or herself from the study (if applicable).

OAT+PET and OAT+PET⁺ participants who miss four consecutive weeks of treatment no longer be eligible to continue in PET but will be eligible to complete follow-up assessments. Furthermore, continued enrollment in standard buprenorphine or methadone maintenance treatment is necessary for patients to continue in PET. Patients who drop out of buprenorphine or methadone maintenance treatment will no longer be eligible for the study and their participation will be terminated. Patients are free not to participate in this study or to withdraw from it at any time. If they decide not to participate in the study, we will be glad to discuss with them other clinically appropriate treatment referrals for PTSD that may be available in Vermont. If patients decide not to participate in this study or to withdraw from this study, their decision will not prejudice their future medical care.

Sources of Materials: Identify sources of research material obtained from individually identifiable human subjects in the form of specimens, records or data. Indicate whether the material or data will be obtained specifically for research purposes or whether use will be made of existing specimens, records or data.

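### Illicit-opioid abstinence is compared by unweighted GEE with no missing-data rule, although participation ends on leaving OAT; unequal, use-related dropout could bias the arm comparison

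*Combined protocol and SAP*

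**What the plan says.** Statistical Methods gives the dichotomous opioid outcomes "repeated measures analyses for dichotomous data based on generalized estimating equations utilizing a logit link function", run in PROC GENMOD, to "compare groups on percentage of participants retained in OAT and abstinent for illicit opioids across Week 4, 8, and 12 assessments". It introduces this as an example and classes the outcomes as exploratory: "Additional secondary outcomes will be exploratory in nature". The threshold of p < .05 applies to all analyses. The section gives no weighting, imputation, coding of missing values or sensitivity analysis for these outcomes.

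Withdrawal Procedures treats two kinds of dropout differently. Patients in the PET arms who miss four consecutive weeks of therapy will "no longer be eligible to continue in PET but will be eligible to complete follow-up assessments". For those who leave OAT, in any arm, the rule is: "Patients who drop out of buprenorphine or methadone maintenance treatment will no longer be eligible for the study and their participation will be terminated".

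The intent-to-treat sentence in Statistical Methods reads "Primary analyses will include all randomized subjects independent of early dropout, consistent with an intent-to-treat approach". It is written for the primary analyses and does not say how a missing binary outcome is coded.

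**The concern.** GEE without weights uses only the records that exist. It is generally valid when data are missing completely at random, or when missingness depends only on covariates in the model, such as arm and visit. Here the event that ends data collection is leaving opioid treatment, which is unlikely to be unrelated to opioid use. The protocol's own background names greater treatment dropout and relapse to illicit use together as poor outcomes of OAT patients with PTSD.

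If an arm loses more patients from OAT, and those patients use more, the remaining patients can look just as abstinent as those in the other arm, or more so. Abstinence and retention are among the few outcomes that show whether adding PET affects opioid treatment. A comparison that hides such an effect would mislead, even as an exploratory result.

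**Working it through.** **Inputs from the documents.** Method: logit-link GEE with no missing-data rule (Statistical Methods). Participation ends on leaving OAT (Withdrawal Procedures). Allocation: 45 per arm (Study Design). The documents give no abstinence rate, no OAT dropout rate and no power figure for these outcomes, so there is no stated figure to reproduce. All rates below are assumptions.

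**1. Size of the hidden difference.** Let p be abstinence among patients still observed, d the proportion who have left OAT, and q abstinence among leavers. Then:

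- rate seen by GEE on observed records = p
- rate in all randomised = (1 − d) × p + d × q

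With p = 0.60 in every arm:

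| d | q = 0 | q = 0.20 | q = 0.60 |
|---|---|---|---|
| 0.10 | 0.90 × 0.60 = 0.54 | 0.54 + 0.02 = 0.56 | 0.54 + 0.06 = 0.60 |
| 0.20 | 0.80 × 0.60 = 0.48 | 0.48 + 0.04 = 0.52 | 0.48 + 0.12 = 0.60 |
| 0.30 | 0.70 × 0.60 = 0.42 | 0.42 + 0.06 = 0.48 | 0.42 + 0.18 = 0.60 |

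The observed records show 60% versus 60% throughout.

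- Leaving 10% versus 30%: the true difference is 54 − 42 = 12 points (q = 0) or 56 − 48 = 8 points (q = 0.20).
- Leaving 10% versus 20%: 54 − 48 = 6 points or 56 − 52 = 4 points.
- Leavers as abstinent as stayers (q = 0.60): nothing is hidden.

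**2. Equal leaving.** With the same d, p and q in both arms, the between-arm error is zero. If observed rates are 60% and 70%, with q = 0.20 and 20% leaving in each arm, the true rates are 0.80 × 0.60 + 0.04 = 52% and 0.80 × 0.70 + 0.04 = 60%. The true difference is 8 points and 10 are shown. The error is therefore small, though the abstinence level in each arm is still overstated.

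**3. Simulation with GEE itself** (two arms, 60,000 subjects, three visits, independence working correlation, assumed rates). Leaving was made more likely in users, and use rose after leaving.

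- About 26% leaving in each arm: Week 12 abstinence was 60–61% on observed records against 51–52% in the full cohort. The between-arm log odds ratio hardly moved (−0.04 observed, −0.03 full).
- 38% versus 16% leaving: the log odds ratio changed sign, from +0.19 in the full cohort to −0.15 on observed records.
- Leaving unrelated to use (about 22% in each arm): observed and full-cohort rates agreed at 57%.

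**4. Would a missing-at-random method repair it?** Not alone. A mixed model, weighted GEE or imputation fills in leavers from stayers with the same history. If stayers with a given history do equally well in both arms, these methods return the same rate in both arms, whatever the leaving rates. No record exists after OAT exit from which a fall in abstinence could be learned.

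**5. Retention.** Leaving OAT is itself the outcome event. With leavers coded as not retained, 10% versus 30% leaving gives 90% versus 70%, an odds ratio of (0.90/0.10) / (0.70/0.30) = 3.86, and nothing is lost. If leavers were set to missing, every observed value would be retained, and the logit model could not be fitted.

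**The case against.** The plan never says that it analyses available cases. It is silent, and counting missing samples as positive is neither planned nor excluded. That is fair: the restriction to observed records is inferred from the named procedure and the absence of any coding rule. But carried out as written, with nothing added, the analysis omits those records.

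Three stronger readings are tempting, and the documents do not support them.

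- **Abstinence is biased.** Between-arm bias needs leaving that differs by arm and is linked to use. The documents give no rates for either, and the 12-point figure assumes no abstinence at all after exit.
- **Retention is biased too, with nearly everyone retained by construction.** A patient terminated for leaving OAT is known to be not retained, and the reading that sets leavers to missing gives a model that cannot be fitted. What is missing is a coding sentence. Only returns to OAT after termination, or loss to follow-up with OAT status unknown, would leave values uncertain.
- **COVID-19 exemptions add informative missingness.** The provision that "urine collection may be excused and study measures can be administered remotely" applies to participants at high risk or with symptoms. Nothing links that to opioid use, other measures can still be taken remotely, and abstinence is not defined as urine-only.

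The exploratory status also stands. No power statement, directional hypothesis or CAPS-5 conclusion depends on these outcomes. That limits the importance of the point but does not remove it, since the results will be tested at p < .05.

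**Conclusion.** The concern holds as a risk of bias in the abstinence comparison. The planned GEE omits missing records, and the withdrawal rule removes exactly the patients who leave OAT. With 60% abstinent among those observed, 10% versus 30% leaving and 0 to 20% abstinent among leavers, a difference of 12 to 8 points is hidden; with 10% versus 20% leaving, 6 to 4 points. With equal leaving, the between-arm bias is close to nil. All of these rates are assumed.

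The main cause is the end of data collection at OAT exit, so a change of model alone does not cure it. For retention, a clarification is enough. The termination rule also sits badly with the intent-to-treat statement. The primary CAPS-5 conclusion does not rest on these exploratory outcomes.

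**What to change.** 1. **Abstinence.** Beside the planned GEE, analyse all randomised participants at Weeks 4, 8 and 12, with values after OAT exit and other missing values counted as not abstinent. Add a sensitivity range for assumed abstinence among leavers, from none up to the observed rate and varied separately by arm. Do not rely on a missing-at-random mixed model, weighted GEE or imputation alone.
2. **Retention.** State that a participant counts as not retained from the OAT dropout date, and say how returns to OAT and unknown OAT status are coded.
3. **Consistency.** Reconcile the termination rule in Withdrawal Procedures with the intent-to-treat statement in Statistical Methods.

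Items 1 and 2 cost wording and programming only. The cost of item 3 depends on how the two passages are reconciled.

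The downside of item 1 is that counting missing as not abstinent can understate abstinence among leavers and so overstate a difference caused by unequal leaving. With 10% versus 30% leaving and p = 0.60, it gives 54% versus 42%, or 12 points, where the true difference is 8 points at q = 0.20 and zero at q = 0.60. The sensitivity range is therefore part of the fix.

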For inclusion in the trial, participants must be >18 years old and be currently maintained on methadone or buprenorphine for OUD. They must also endorse >1 traumatic event on the Life Events Checklist for DSM-V (LEC-5; Weathers et al., 2013) and meet current DSM-V PTSD criteria (American Psychiatric Association, 2013) based on the Clinician Administered PTSD Scale for DSM-5 (CAPS-5; Weathers et al., 2013). Participants also must be willing to have therapy sessions audio recorded for the purpose of completing weekly homework assignments and have clear memory for the traumatic event. Consistent with our prior IRB-approved studies among OAT-enrolled patients, eligible participants must be maintained on a stable methadone or buprenorphine dose for >1 month prior to the study (Dunn et al., 2008, 2010; Sigmon et al., 2016ab). At intake, participants will sign a written release to allow study staff to confirm medication dose and clinical stability with the participant's OAT provider.

Individuals with an acute psychotic disorder, bipolar disorder with an active manic episode (but not simply the presence of bipolar disorder), imminent risk for suicide, a medical condition that may interfere with consent or participation (e.g., organic brain syndrome, dementia, head injury, neuropathy, etc.) will be excluded, as well those who demonstrate illiteracy in English. Participants must provide written informed consent to participate. Those meeting the above criteria and interested in the study will be eligible to participate. Individuals who meet the study criteria described above and provide written informed consent will be eligible to participate.

Experimental conditions.

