Protection Against Risk: (1) All study data will be confidential. The following steps will be taken to minimize risks to confidentiality: (a) a UVM-supported platform (Zoom) will be used any time that study procedures are conducted remotely to provide the highest level of privacy and security for the participant; (b) assessment data and treatment record forms will be kept in locked cabinets at the UVM research office; (c) participant identity will be disguised using ID numbers keyed to a master list; (d) session recordings of therapy sessions will be transferred to the secure UVM College of Medicine server; (e) data will be entered directly onto computer files that will be password protected; and (f) computer files will carry only participant numbers for case identification. All project staff will be trained in the importance of confidentiality. When the results of the study are published, data that might reveal the identity of a participant will be disguised.

(2) Patients are free not to participate in this study or to withdraw from it at any time. Participants who are determined to be ineligible based on exclusion criteria or who do not consent to participation in the study will be offered clinically appropriate treatment referrals outside the study. If patients decide not to participate in this study or to withdraw from this study, their decision will not prejudice their future medical care at UVM or UVM Medical Center. The investigator also retains the right to terminate patients' participation in the study if in their judgment continued participation would put them in physical or psychological danger. Additional details on our data and safety monitoring of the proposed research to ensure the safety of subjects is provided in the below section entitled "Data and Safety Monitoring Plan".

(3) Participants' reactions to study assessment and treatment will be closely monitored and negative reactions will be addressed therapeutically. To avoid or reduce mild to moderate emotional discomfort or frustration associated with psychiatric interviews and questionnaires, participants will be allowed breaks as needed during the intake and follow-up assessments. Additionally, intake assessments can be spaced over multiple visits, if needed.

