(4) Prior to beginning PET, informed consent will be obtained from eligible participants to reduce the possible risks of mild to moderate anxiety when exposed to anxiety-provoking images and situations in treatment sessions, at home or completing homework exercises. Each participant will be given a rationale for PET and advised of the treatment procedure and the temporary effects that the procedure might have. Participants will be required to give consent prior to every exposure exercise or task. PET has well-documented efficacy for reducing PTSD symptom severity (Foa et al., 1999, 2005, 2008; Powers et al., 2010). While a small proportion of individuals fail to benefit from PET, very few report adverse effects. The exposure exercises will be individually and gradually titrated such that in-vivo exposure exercises start with real-life trauma reminders that elicit moderate anxiety and progress to more anxiety-provoking stimuli.

(5) Participants in each condition will be informed by study staff that they may call between sessions should they experience a crisis or are distressed enough to need psychological support. If a therapist becomes concerned about a participant's psychological welfare, contact will be made with the PI who will arrange for psychological evaluation. Although unlikely, if substantial emotional reactions develop that require additional interventions, participants will be withdrawn from the study and referred to public health treatment providers to receive these services. Such identification can be made by research therapists in consultation with the PI.

(6) In cases where danger to self or others is identified, the participant will be withdrawn from the study and clinically appropriate emergency service procedures will be implemented. In cases where a participant is determined to be a danger to self or others, the PI or qualified study staff member will assess the individual's level of risk and work with the participant to develop a safety plan. Study staff will also provide the participant with relevant educational material, contact information for national and local crisis services, and referrals to local counseling services. In cases where a participant is determined to be at imminent risk for harm to self or others, the PI will make referrals for more intensive psychiatric services and arrange for transportation to these facilities when necessary.

(7) Risks associated with OAT as usual may include non-reduction of PTSD symptoms.

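### The safety rules in Protection Against Risk, items (5) and (6), remove participants from the whole study and not only from PET, with no provision for the remaining CAPS-5 and adverse event assessments

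*Combined protocol and SAP*

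**What the plan says.** All places are in the combined protocol and SAP.

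- **Protection Against Risk, item (5).** If a serious emotional reaction calls for further intervention, "participants will be withdrawn from the study and referred to public health treatment providers to receive these services". The item calls this unlikely. Its first sentence addresses participants in every condition.
- **Protection Against Risk, item (6).** "In cases where danger to self or others is identified, the participant will be withdrawn from the study". The same sentence adds emergency measures. The next sentences describe assessing the level of risk and making a safety plan. A last sentence sets out a further step, beginning "In cases where a participant is determined to be at imminent risk for harm to self or others". No arm is named.
- **Protection Against Risk, items (2) and (3).** The investigator may already end participation "if in their judgment continued participation would put them in physical or psychological danger". To limit distress, "participants will be allowed breaks as needed during the intake and follow-up assessments".
- **Withdrawal Procedures.** PET participants who miss four weeks in a row will "no longer be eligible to continue in PET but will be eligible to complete follow-up assessments". The same section ends participation for anyone who leaves opioid agonist treatment (OAT). The triggers in items (5) and (6) are not mentioned there.
- **Adverse event section.** Adverse events are assessed at clinic visits.
- **Statistical Methods.** The primary analysis is intent-to-treat, using a mixed model of CAPS-5 at Weeks 4, 8 and 12.

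**The concern.** Stopping a therapy and leaving a trial are different events. For missed sessions the protocol separates them, but for the two safety triggers it does not. The people removed are among those whose outcomes a reader would most want to see, because they became distressed or dangerous during the study. Including all randomized participants in the analysis does not supply visits that were never held. The mixed model relies on data being missing at random, which is doubtful if the reason for removal is a deterioration that no recorded CAPS-5 shows.

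Two things are at stake: the description of how these participants fared by Week 12, including the later course of their adverse events, and possibly the Week 12 comparison, if removals are unequal between arms.

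**Working it through.** **1. The text side by side**

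| Event | PET | Follow-up assessments |
|---|---|---|
| Four consecutive missed weeks (Withdrawal Procedures) | stops | continue |
| Leaves OAT (Withdrawal Procedures) | stops | end; participation terminated |
| Serious emotional reaction, item (5) | stops | withdrawn from study; nothing further stated |
| Danger identified, item (6) | stops | withdrawn from study; nothing further stated |

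The first row shows that the protocol says so when it means follow-up to continue. That makes an end to assessment the natural reading of the last two rows, though no sentence states it.

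**2. The item (6) threshold.** Withdrawal comes first, assessment of the level of risk second, and imminent risk is a separate step. So withdrawal most naturally covers danger that is not imminent. The coupling to emergency measures points the other way, so some ambiguity remains. If the wider reading is right, there is an asymmetry with entry, where the exclusion is "imminent risk for suicide, a medical condition that may interfere with consent or participation": a person with non-imminent danger could be enrolled and then removed once it was identified.

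**3. Which visits are lost.** Under OAT + PET, the first in vivo exercise is assigned at Session 3 and imaginal exposure starts at Session 4. An exposure-driven reaction would therefore tend to cost Weeks 8 and 12, or Week 12 alone. Item (6) is not tied to exposure and can arise at any time in any arm.

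**4. Scale from the plan's own figures.** Sample Size Justification gives 80% power, alpha .05 and 8 CAPS-5 points; Study Design gives 45 per arm. No SD is stated, so the 80% cannot be reproduced independently. Back-solving (two-sided test assumed):

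- Normal approximation: SD = 8 / [(1.960 + 0.842) × √(2/45)] = 13.5. With the t-test: 13.4.
- SE of a difference = 13.4 × √(2/45) = 2.82.
- Power falls little: 79.1%, 78.1% and 77.2% if 1, 2 or 3 per arm are lost.

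**5. Shift in the arm difference.** If k_A and k_B participants are removed from two arms of 45, and their unseen Week 12 scores are d points worse than those of participants who stay, then shift = (k_A − k_B)/45 × d. All k and d are assumed.

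| Net excess | d | Shift | Share of 8 | In SE |
|---|---|---|---|---|
| 1 | 5 | 0.11 | 1.4% | 0.04 |
| 1 | 15 | 0.33 | 4.2% | 0.12 |
| 2 | 10 | 0.44 | 5.6% | 0.16 |
| 2 | 15 | 0.67 | 8.3% | 0.24 |
| 3 | 15 | 1.00 | 12.5% | 0.35 |

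The shift favours the arm that loses more people, and it is zero if losses balance.

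**6. What the model recovers.** For a random-intercept model with within-person correlation r (assumed 0.3 to 0.7), the share recovered depends on what was observed and on whether baseline is one of the outcomes. Statistical Methods names Weeks 4, 8 and 12 but also contrasts on change from baseline, so both cases are shown.

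| Worsening recorded at | Lost | Baseline an outcome | Only Weeks 4, 8, 12 modelled |
|---|---|---|---|
| no visit | any | 0% | 0% |
| Week 4 | Weeks 8, 12 | r/(1+r): 23% to 41% | r: 30% to 70% |
| Week 8 but not Week 4 | Week 12 | r/(1+2r): 19% to 29% | r/(1+r): 23% to 41% |
| Weeks 4 and 8 | Week 12 | 2r/(1+2r): 38% to 58% | 2r/(1+r): 46% to 82% |

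Example, 3 against 1 removed at 15 points: 0.67 with no recovery. With baseline as an outcome, 0.39 to 0.54 remains after one worsened visit and 0.28 to 0.42 after two. With only Weeks 4, 8 and 12 modelled, 0.20 to 0.47 remains when Week 4 is the only visit seen and is worsened, and 0.12 to 0.36 when Weeks 4 and 8 both are.

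**The case against.** The strongest reply is that this is a clinical safety decision. Someone just identified as dangerous should not be pressed into another trauma interview, possibly by a bachelor's-level assistant or over a remote link that the protocol says raises confidentiality risk. That stands for anyone who cannot be assessed safely. But the investigator's discretion in item (2) already covers that person, so the mandatory rule mainly adds the loss of people who could be assessed safely. The objection does show that the fix needs clinical clearance built in.

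Three stronger readings are tempting, and the documents do not carry them.

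- A reader might infer that the protocol forbids collecting later data. It does not say so; the end of assessment is inferred from the withdrawal wording and the contrast with missed sessions.
- A reader might take non-imminent danger as a settled trigger. It is the better reading, but the link to emergency measures leaves doubt.
- A reader might conclude that the rule biases the trial toward PET. An exposure-driven excess is plausible mainly in OAT+PET+: unincentivised participants in the methadone trial cited under Purpose averaged 1.80 sessions, so few comparable participants would reach Session 4. Weekly therapist contact could raise detection in both PET arms. Yet danger can arise in any arm and could be more frequent in OAT, for which item (7) says: "Risks associated with OAT as usual may include non-reduction of PTSD symptoms". Nor is danger to others the same thing as a worse CAPS-5 score, and the protocol describes PET distress as temporary.

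**Conclusion.** The point holds as a modest one. Items (5) and (6) withdraw participants in any arm from the study, and neither provides for later assessment. On the natural reading, their remaining CAPS-5 interviews and visit-based adverse event checks end. The likely cost is descriptive: the Week 12 outcome and later safety course of these participants would be unknown. The event itself would still be managed, and reported if serious.

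No material effect on the primary comparison is shown. The calculated shift is 0.1 to 1.0 CAPS-5 points (0.04 to 0.35 SE) before recovery. It rests on an assumed net excess of 1 to 3 of 45 and an assumed deficit of 5 to 15 points; the protocol gives neither and calls the item (5) event unlikely. Recovery is nil if worsening follows the last visit. If worsening was recorded, recovery is about 19% to 58% with baseline as an outcome. It is 30% to 82% if only Weeks 4, 8 and 12 are modelled and every observed visit showed the worsening. Direction is unknown. The termination rule for leaving OAT is a separate matter. This is an optional, low-cost improvement.

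**What to change.** In items (5) and (6), replace withdrawal from the study with wording such as: PET, where assigned, will be stopped and the participant referred or given emergency care as now described; participants in any condition remain eligible for the scheduled Week 4, 8 and 12 assessments and the adverse event checks at those visits, remotely where appropriate, unless they withdraw consent or the investigator considers that they cannot safely be assessed.

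Leave item (2) unchanged. Report safety discontinuations by arm, with the last CAPS-5 visit obtained for each.

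Cost: a protocol and consent amendment, some staff time, and clearance by the principal investigator or a therapist before an at-risk participant is assessed. No new visits are scheduled. For the four removals in the 3-against-1 example, all after Week 4, at most 4 × 2 = 8 further assessments would be paid. That is 8 × $50 = $400 if the stated $150 covers all three follow-up visits, or 8 × $150 = $1,200 if it is paid per visit. Remote assessment carries a somewhat higher confidentiality risk, and some of these participants will decline.
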